6.3. Randomisation, blinding and code-breaking

A 'minimisation' sampling procedure will be used, whereby participants' stuttering severity as measured during screening with the SSI-4 will be used to assign successive participants to true stimulation or sham stimulation, minimising group differences in severity. A member of the Departmental of Experimental Psychology who is not involved with the study will be in charge of communicating to the project team what code they should use.

On the basis of this randomisation, half the participants will receive true tDCS stimulation and the other half will be in a control group that will not receive stimulation (sham tDCS). In sham tDCS the current is applied for a sufficiently brief duration to avoid any change in cortical

excitability (up to 30 seconds) but long enough to produce the transitory sensation on the skin associated with real tDCS. Although the stimulation is different, each participant will receive exactly the same speech training throughout the study.

The study will also be double-blinded, meaning that the researchers, study staff, and participants will not know whether the condition involves real or sham tDCS. The stimulator used in the study has a 'study' mode to allow the operator to be blind to the stimulation condition.

The person in charge of the randomisation procedure will have the capacity to unblind the data for analysis once data collection is complete. Data may be unblinded during the data collection only in the context of a serious adverse event potentially related to the type of stimulation or if a patient withdraws from the study and needs to be replaced.

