9.2. The Number of Participants

We plan to recruit 40 PWS and up to 30 controls. The sample size was determined based on previous cross-sectional studies in stuttering, including our own. A sample size of 20 participants in each group is higher than most previous behavioural and functional imaging studies in PWS. This should ensure sufficient sensitivity to detect differences in behaviour, brain structure and function. It should also allow us to determine the relationship between the experimental variables and other measures such as stuttering severity and duration of stuttering. A sample size of 20 for each group should detect a group difference with an effect size of 0.9 at 80% power and 5% false positive rate. For the tDCS study across 5 days, we will compare two groups of 20 PWS. In our previous study, with sample sizes of 15 in each group, effect sizes of 0.93 and 0.50 were obtained for the reduction in the SSI at 1 week and 6 weeks post intervention.

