We are including the Beck Anxiety Inventory to monitor for any differences in anxiety between the groups, which should be minimized at baseline by the randomization procedure. Any effect of the intervention of stuttering severity may also have consequences for anxiety. We will assess the change in anxiety scores with the same analysis as planned for the primary outcome measure. We will also examine the correlation of the change in anxiety score and the change in (i) stuttering severity (SSI-4), and percentage of disfluent syllables on (ii) reading and (iii) conversation tasks

The Premonitory Awareness in Stuttering Scale (PAiS) tests for anticipation of stuttering events. We have included this as an exploratory measure. We also include subjective ratings of stuttering severity and speech naturalness, and an objective measure of speech naturalness. For each scale (PAiS, subjective severity, subjective naturalness, objective naturalness) change scores will be analysed as described for the primary outcome measure.

In addition, we include exploratory analysis of the effects of tDCS during the intervention period. Effects of tDCS immediately after intervention will be analysed using change in percentage of disfluent syllables (baseline subtracted) measured post-intervention on each day, for both reading and conversation. A mixed model ANOVA will be used with stimulation group (tDCS, sham) as the between subjects factor and time point (day 1 to 5) and task (reading, conversation) as the within-subjects factors. Carry-over of effects following a period including sleep will be analysed using change in percentage of disfluent syllables (baseline subtracted) measured immediately before the intervention, for both reading and conversation. A mixed model ANOVA will be used with stimulation group (tDCS, sham) as the between subjects factor and time point (day 2 to 5) and task (reading, conversation) as the within-subjects factors. The Day 1 time point will be omitted in this analysis, as no intervention will have been performed prior to that measurement.

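### The SAP does not say how arm enters the anxiety–stuttering correlations, and it analyses change in the Beck Anxiety Inventory without baseline anxiety as a covariate

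*SAP*

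**What the plan says.** Under the heading on other pre-specified measures, the SAP includes the Beck Anxiety Inventory (BAI) to watch for anxiety differences between the groups. It says of those differences: "which should be minimized at baseline by the randomization procedure". It allows that an effect on stuttering could carry over to anxiety. Change in BAI is to be analysed in the same way as the primary outcome, that is, by a mixed ANOVA of baseline-subtracted scores with stimulation group and time point. No baseline covariate is named, and the opening of the SAP adopts change scores for all variables for consistency.

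The SAP then states: "We will also examine the correlation of the change in anxiety score and the change in (i) stuttering severity (SSI-4". The other two stuttering measures are the percentages of disfluent syllables in reading and in conversation. The sentence does not mention arm, time point or type of coefficient.

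Protocol section 6.3 describes the allocation: "participants' stuttering severity as measured during screening with the SSI-4 will be used to assign successive participants to true stimulation or sham stimulation". Its stated aim is "minimising group differences in severity". No other balancing factor appears. Appendix B first schedules the BAI at the baseline visit, not at screening.

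**The concern.** Two linked analyses are left weaker than they need to be.

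The first is the correlation. When two outcomes both differ by arm, a correlation over all participants mixes the difference between arms with the association within arms. A reader of the result wants to know whether people whose stuttering fell more also became less anxious. A pooled figure can suggest this when the two outcomes merely both shifted with treatment. It can also hide a real link if the shifts run in opposite directions. The SAP itself expects group effects on reading and conversation and regards an effect on anxiety as possible, so the question of arm is not remote.

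The second is the comparison of BAI change between arms. Minimisation on SSI-4 gives anxiety little protection against chance imbalance at this sample size, yet the SAP credits the allocation with keeping anxiety differences small. Baseline BAI is collected but used only by subtraction. An observed gap would therefore pass in part into the comparison of change.

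**Working it through.** **Inputs from the documents.** There are 20 per arm ("For the tDCS study across 5 days, we will compare two groups of 20 PWS", protocol section 9.2), allocated 1:1. The same section gives effects of 0.93 and 0.50 for the SSI reduction at 1 and 6 weeks in the previous study.

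**Assumptions, because the documents give no figure.** Standardised effect on BAI change: 0.2 to 0.93. Correlation of BAI with SSI-4: 0 to 0.5. Correlation of baseline with follow-up BAI: 0.6, with equal variances.

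**The plan's own figure.** Section 9.2 states "effect size of 0.9 at 80% power and 5% false positive rate" for 20 per group. The two-sided normal approximation returns 20 per arm (power 81.2%). The exact t calculation gives power 79.2% and a detectable effect of 0.909. The figure reproduces. It does not concern BAI, and the plan states no figure for the correlations or for baseline anxiety.

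**Pooled correlation.** Let the arm effects be dx (stuttering) and dy (BAI), in within-arm SD units, and let the within-arm correlation be w. With equal arms:

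pooled r = (w + dx·dy/4) / √[(1 + dx²/4)(1 + dy²/4)]

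Example with w = 0, dx = 0.93, dy = 0.5: 0.11625 / √(1.2162 × 1.0625) = 0.11625 / 1.1368 = 0.102.

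The table gives r from the formula, with rejection rates at nominal 5% from 40,000 simulated trials per setting, all with w = 0:

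| SSI effect | Assumed BAI effect | Pooled r | False positives |
|---|---|---|---|
| 0.50 | 0.2 | 0.024 | 5.1% |
| 0.50 | 0.5 | 0.059 | 6.4% |
| 0.50 | 0.8 | 0.090 | 8.5% |
| 0.50 | 0.93 | 0.102 | 9.5% |
| 0.93 | 0.2 | 0.042 | 5.8% |
| 0.93 | 0.5 | 0.102 | 9.9% |
| 0.93 | 0.8 | 0.157 | 16.3% |
| 0.93 | 0.93 | 0.178 | 19.8% |

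If the BAI effect is zero, r is 0 and the rate stays at about 5%; by the formula the same holds if the stuttering effect is zero. Centring both changes on their arm means gives mean r of 0.00 and rejection of 4.8% to 5.1% throughout. The critical |r| at n = 40 is 0.31, so the inflation alone does not reach significance on average.

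**Anxiety effect wholly through stuttering.** Take w = 0.3 and dx = 0.93, so dy = 0.3 × 0.93 = 0.279. Pooled r = (0.3 + 0.0649) / √(1.2162 × 1.0195) = 0.33, against 0.30 within arm.

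**Opposite directions.** With w = 0.3, dx = 0.93 and dy = −0.5, pooled r = (0.3 − 0.11625) / 1.1368 = 0.16, so a real association is roughly halved.

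**Chance gap in baseline BAI.** If SSI-4 is balanced and its correlation with BAI is ρ, the SD of the standardised difference is √(2/20) × √(1 − ρ²).

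- ρ = 0: SD 0.316; P(gap above 0.5 SD) = 2[1 − Φ(0.5/0.316)] = 11.4%
- ρ = 0.3: SD 0.302; 9.7%
- ρ = 0.5: SD 0.274; 6.8%

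**Effect on the change score.** Given a 0.5 SD gap and no treatment effect, the expected difference in change is (1 − 0.6) × 0.5 = 0.20 baseline SD, in favour of the arm that started more anxious.

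**Precision.** In units of the BAI variance, the change score has variance 2(1 − 0.6) = 0.80. With baseline as a covariate the residual variance is 1 − 0.6² = 0.64. The ratio is 0.64/0.80 = 0.80, a fifth less before the loss of one degree of freedom.

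**The case against.** The strongest reply is that the SAP nowhere commits to a pooled, unadjusted correlation. That is right. A reader might infer such a commitment, because the SAP names stimulation group in its other analyses and not here, but silence is an omission and not a stated method.

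A reader might also infer that a treatment effect on both outcomes necessarily produces a false association. The documents do not support this. The SAP's own idea is that anxiety may respond to the change in stuttering. On that view the within-arm association is real and pooling barely alters it. The artefact needs tDCS to act on anxiety by a separate route, which the documents do not propose.

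On size, the 20% rate needs an anxiety effect as large as the earlier 1-week SSI effect. With the earlier 6-week effect of 0.50, rates run from 5.1% to 9.5%.

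On baseline anxiety, some imbalance is ordinary chance at 20 per arm, and nothing in the allocation favours one direction. Over repeated allocations the change score is unbiased, so a reader should not conclude that the BAI comparison is biased by design. The SAP's remark on balance is too strong rather than baseless. Preferring a baseline covariate is also a general argument, since change scores are used throughout.

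All of this limits the size of the point. None of it favours leaving the text as it stands: adjusting for arm keeps a real within-arm link and removes the artefact, and the covariate uses data that the trial already collects.

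**Conclusion.** The point holds as a minor one with two parts. First, the handling of arm in the three correlations is unspecified. If they are run pooled, and the effects on anxiety and stuttering are unrelated within arm, mean r is about 0.02 to 0.18 and false positives about 5% to 20%. The inflation is slight if anxiety follows stuttering and absent if either effect is zero. Second, BAI change is analysed without baseline BAI, although allocation balances only screening SSI-4. A baseline gap above 0.5 SD arises by chance in about 7% to 11% of trials. A gap of 0.5 SD carries an expected 0.20 SD into the difference in change, and the analysis is less precise than it could be even without a gap.

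The BAI effect, the BAI–SSI-4 correlation and the 0.6 are assumptions. BAI is an other pre-specified measure, so the primary outcome, the secondary outcomes and the sample size are not affected.

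**What to change.** Three changes to the BAI paragraph of the SAP:

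1. Compute each of the three correlations as a partial correlation adjusted for arm, or as a pooled within-arm correlation. Use a rank-based version if the data are non-normal, in line with the SAP's general rule; ranking alone does not deal with arm. State the time point or points used.
2. Add baseline BAI as a covariate to the group-by-time analysis of BAI change.
3. Reword the sentence on baseline anxiety to say that allocation minimises differences in screening SSI-4 and balances anxiety only in expectation.

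The cost is one degree of freedom per adjustment and a few lines of text. Baseline BAI is already in the schedule, so no new data are needed.

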1. SYNOPSIS

Study Title	Investigating non-invasive brain stimulation to enhance fluency in people who stutter
Internal ref. no. / short title	INSTEP Trial
Study Design	Double-blind randomised controlled trial. Active treatment: bi-hemispheric tDCS, Control: Sham tDCS. Minimisation randomisation.
Study Participants	Healthy adult males with developmental stuttering and healthy male controls with no speech disorders
Planned Sample Size	70 (40 participants with developmental stuttering, 30 control participants)
Planned Study Period	1 st November 2017 – 30th April 2020
	Outcome Measures
Primary	Change from baseline (i.e. baseline subtracted) in a clinical measure of stuttering severity (SSI-4), post training (1 week, 6 weeks, and 3 months after training).
Secondary	Change from baseline (i.e. baseline subtracted) in: (i) % disfluent syllables produced during conversation; (ii) % disfluent syllables produced during reading post training (1 week, 6 weeks, and 3 months after training). (iii) total score on an attitudinal measure (OASES), post training (6 weeks, and 3 months after training).
Other Pre-specified	Change from baseline (i.e. baseline subtracted) in: (i) total score on the Premonitory Awareness in Stuttering Scale; (ii) total score on the Beck Anxiety Inventory; (iii) subjective and objective ratings of stuttering severity and naturalness, post training (1 week, 6 weeks, and 3 months after training). Changes from baseline (i.e. baseline subtracted) % disfluent syllables produced during (i) conversation and (ii) reading, during the 5-day training (immediately post intervention days 1 to 5; immediately pre-intervention days 2 to 5).
	Exploratory (non-behavioural) measures
Other	We will use MRI and TMS, to evaluate neural structure, function, and excitability in people who stutter and in healthy controls. Using MRI, we will also obtain images of the vocal tract during speech. These measurements will be obtained just before training begins and 1 week after the end of the training in people who stutter and once only in healthy controls.

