6.5. Subsequent Visits

Visits 2-6 [Days 3-7]

These visits may take place at University testing facilities, or at the participant's home or office and will take place at the same time on each day. Participants will complete a short speech fluency assessment during reading and conversation at the start and end of the session; this assessment will be video recorded. A safety screening for tDCS will be conducted to ensure that the participant is not experiencing any discomfort/ risk, and to check that eligibility has not been compromised (for example, by use of medication). The intervention will then be delivered (sham vs. true tDCS + speech fluency training). The speech fluency training lasts approximately 40 minutes and stimulation is delivered for 20 minutes at the start of the training. Each session should last no more than one hour on each of the five days of intervention.

Visit 7 [Days 14-15]:

This visit will take place at OHBA. We will obtain behavioural measures of speech fluency, as well as complete clinical assessments (SSI-4). Following this, participants will repeat the brain and vocal tract imaging assessments (MRI and TMS) described. Standard operating procedures and safety guidelines for each of these procedures will be followed.

Visit 8 [+6 weeks following Visit 6]

This visit will be conducted via videoconference. We will obtain behavioural measures of speech fluency, as well as complete clinical assessments (SSI-4, OASES).

Visit 9 [+3 months following Visit 6]

This visit will be conducted via videoconference. We will obtain behavioural measures of speech fluency, as well as complete clinical assessments (SSI-4, OASES).

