7. INTERVENTIONS

A five-day intervention with tDCS (bi-hemispheric vs. sham) combined with speech fluency training will be carried out.

tDCS: Participants will receive five daily sessions of real tDCS combined with speech training, or sham stimulation combined with speech training, according to which arm of the trial they are randomly assigned. Stimulation will be applied for no more than 20 minutes per session. Stimulation will be carried out in accordance with the protocol for the Central University Research Ethics Committee for use in healthy volunteers. Our study will be carried out in accordance with procedures outlined in the SOP and will not exceed the recommendations of the approved protocol. Please see section 7.6 for addition information regarding tDCS procedure.

Speech fluency training: Participants will complete speech tasks whilst speaking to an external beat (metronome-timed speech). Different tasks will be used during the 20 minutes of stimulation and repeated for a further 20 minutes once the stimulation has ended. The order of tasks will be randomised across the five days of speech training. The duration of each training session will be one hour, and participants will receive concurrent tDCS for 20 minutes at the start of the fluency training. Participants will also complete brief speech tasks before and after the training.

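### On training Days 2 to 5 the planned immediate tDCS effect includes any carry-over from earlier sessions, and no planned analysis tests the within-session change

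*SAP*

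**What the plan says.** The SAP, under Other pre-specified measures, states: "we include exploratory analysis of the effects of tDCS during the intervention period". Two analyses follow.

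- **Immediate effect.** "Effects of tDCS immediately after intervention will be analysed using change in percentage of disfluent syllables (baseline subtracted) measured post-intervention on each day". The model is a mixed ANOVA with stimulation group between subjects and "time point (day 1 to 5) and task (reading, conversation) as the within-subjects factors".
- **Carry-over.** "Carry-over of effects following a period including sleep will be analysed using change in percentage of disfluent syllables (baseline subtracted) measured immediately before the intervention". This is a separate ANOVA of the same form, limited to Days 2 to 5: "The Day 1 time point will be omitted in this analysis, as no intervention will have been performed prior to that measurement".

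The protocol synopsis lists both among the other pre-specified measures. It defines both as changes from baseline, at these times: "immediately post intervention days 1 to 5; immediately pre-intervention days 2 to 5".

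Protocol section 6.5 sets out what is recorded at each training visit: "Participants will complete a short speech fluency assessment during reading and conversation at the start and end of the session". A same-day pair of samples therefore exists for each of the five days. Neither document plans a post-session minus same-day pre-session difference, a pre-session covariate, or a pre/post factor.

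**The concern.** The SAP treats the effect straight after a session and the carry-over after sleep as separate topics, yet it scores both against one baseline. Stimulation is repeated: "Participants will receive five daily sessions of real tDCS combined with speech training, or sham stimulation combined with speech training". If some of the benefit of tDCS lasts overnight, the post-session score on Days 2 to 5 holds that retained benefit as well as whatever the day's session added.

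Both arms receive the same speech training (protocol section 6.3), so retained training benefit common to the arms cancels in the group contrast. Only carry-over specific to tDCS remains in it. The risk is one of interpretation. A group effect labelled immediate could partly or largely reflect earlier sessions, and a group by day interaction could mean either accumulation or a changing response within sessions.

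**Working it through.** **Plan's own figure.** The documents give no number on this point. Their only design calculation (20 per group, effect size 0.9, 80% power, 5% error; protocol section 9.2) reproduces as two-sided: n = 20, with power 81.2% by the normal approximation and 79.2% by noncentral t. Nothing below depends on it.

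**Step 1: which baseline.** The SAP does not say which sample is the baseline for these scores. Protocol section 6.4 and Appendix B point to Visit 1. It cannot be the same-day pre-session sample, because the carry-over score would then be zero by construction. Whether it is Visit 1 or the Day 1 pre-session sample does not matter for what follows.

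**Step 2: the identity.** For day k,

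(post_k − baseline) = (pre_k − baseline) + (post_k − pre_k).

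The left side is the SAP's immediate score. The first term on the right is its carry-over score. The second is the within-session change, which no planned analysis tests. The same identity holds for the tDCS-minus-sham contrasts. On Day 1 no session has yet been given, so the expected contrast in the first term is zero.

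**Step 3: size under an assumed retention.** Let the within-session tDCS-minus-sham effect be 1 unit in every session, and let a fraction r of the accumulated effect survive each night (r is an assumption, full range 0 to 1). Then pre_1 = 0, pre_k = r × post_(k−1), and post_k = pre_k + 1.

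| r | Post minus baseline, Days 1 to 5 | Sum | Mean (sum/5) | Carry-over share (mean − 1)/mean |
|---|---|---|---|---|
| 0 | 1, 1, 1, 1, 1 | 5 | 1.00 | 0% |
| 0.25 | 1, 1.250, 1.312, 1.328, 1.332 | 6.22 | 1.24 | 20% |
| 0.5 | 1, 1.500, 1.750, 1.875, 1.938 | 8.06 | 1.61 | 38% |
| 0.75 | 1, 1.750, 2.312, 2.734, 3.051 | 10.85 | 2.17 | 54% |
| 1 | 1, 2, 3, 4, 5 | 15 | 3.00 | 67% |

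Post minus same-day pre averages 1.00 in every row.

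**Step 4: an extreme pattern.** Suppose tDCS acts only in session 1, with effect 1, and a fraction r is then held without further loss. Post minus baseline shows r on each of Days 2 to 5, while post minus same-day pre shows 0 on those days. At r = 0.5 the five-day means are (1 + 4 × 0.5)/5 = 0.6 and 1/5 = 0.2.

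**The case against.** **Timing reading.** The SAP never says that it means to isolate a single session. Its wording may only describe when speech was measured: straight after stimulation in one analysis, after a night's sleep in the other. Both are then valid randomised comparisons of status against a common baseline. This stands, and it is why the planned analysis should be kept. However, setting it beside a carry-over analysis invites the reading that it captures the session's own effect, so it needs a clearer label.

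**The information is recoverable.** A reader might infer that the plan cannot tell an acute from a cumulative effect at all. The documents do not support that. Day 1 is free of earlier sessions, day is a factor, and the two ANOVAs share a baseline. With complete data, the Day 2-5 post contrasts minus the pre contrasts give the within-session point estimates. A benefit arising purely overnight would show as no Day 1 contrast and equal pre and post contrasts afterwards. What is missing is a planned test of the paired difference, and a planned reading of Day 1 alone.

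**Pre-session data are used.** This is true for Days 2 to 5, in the carry-over ANOVA. They are never paired with the same day's post-session sample. Leaving Day 1 out of the carry-over time points is correct.

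**Exploratory status.** This also stands. No primary or secondary conclusion rests on these analyses.

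**Conclusion.** The point holds as a modest, inexpensive improvement to an exploratory analysis. From Day 2 the immediate score contains the SAP's own carry-over score; this is an identity and needs no assumption. How much it matters depends on tDCS-specific overnight retention, which the documents do not give. Under the geometric model the five-day mean contrast ranges from 1.00 times the within-session effect (nothing retained) to 3.00 times (everything retained).

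Three stronger readings should be resisted.

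- **A fixed inflation, such as a doubling.** No single factor is supported, because the figure moves with both the retention value and the carry-over model.
- **A guaranteed gain in precision from same-day pairing.** That would rest on correlations between samples that the documents do not report.
- **A mismatch of place between baseline and training samples.** Section 6.4 puts Visit 1 at the imaging centre, but section 4 allows live components to be done at the participant's home or office, and section 6.5 does not promise one venue across training days.

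**What to change.** 1. Add to the SAP, as the immediate-effect analysis, a group by day (1 to 5) by task mixed ANOVA of post-session minus same-day pre-session percentage of disfluent syllables.
2. Keep the planned post-session minus baseline analysis and label it cumulative post-session change.
3. Leave the planned carry-over analysis as it is.
4. Make the protocol synopsis match, since it defines both training-period measures as changes from baseline. The edit therefore touches both documents.

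No new data are needed: the samples are already scheduled, and section 6.6 has the recordings from every visit scored offline. The cost is a few sentences and one further exploratory analysis. Its outcome is a difference between two short speech samples, which may be noisy. The SAP's existing rules on outliers and non-normal variables can apply to it unchanged.
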